#### 6.6 Artemisinins display anti-angiogenic effects

Angiogenesis plays a vital role in cancer cell growth and development. Isolated tumor cells without an adequate nutrition and oxygen supply display a growth restriction of about  $1-2~\text{mm}^3$ . Cancer cells require proangiogenic stimuli such as metalloproteinase (MMP) and vascular endothelial growth factor (VEGF) and a reduction in anti-angiogenic factors such thrombospondin and tissue inhibitor of metalloproteinase (TIMP) to maintain a viable blood supply required for growth (Hanahan & Weinberg., 2011). Under hypoxic conditions, hypoxia induced factor (HIF- $1\alpha$ ) and nuclear factor-kB (NF-kB) are activated resulting in transcription of VEGF and angiogenesis. Artemisinins were shown to reduce the levels of HIF- $1\alpha$  and VEGF in mouse embryonic stem cells (Wartenberg *et al.*, 2003). In a mouse lung carcinoma model, administration of artemisinin resulted in a reduction in VEFG-C and lymphangiogenesis (Wang *et al.*, 2008). Artesunate also suppressed levels of VEGF and KDR/flk-1 resulting in reduced tumor growth in BALB/c nude mice implanted with human ovarian cancer cells (Chen *et al.*, 2004), in Kaposi's sarcoma (KS-IMM) xenograft mice (Dell'Eva *et al.*, 2004) and in a rat glioma model (Wu et al., 2009). Artesunate was also shown to exert anti-angiogenic effects on renal cancer cells in vitro in a dose-dependent manner (Jong *et al.*, 2015). Following treatment with artesunate, renal cell tumours in subcutaneous xenografts models showed decreased levels of proliferation marker Ki-67 and reductions in mean microvessel density compared to controls.

#### 6.7 Artemisinins block tissue invasion and metastasis

A key hallmark of cancer cells is their ability to detach from the primary tumour, degrade the extracellular matrix and metastasise through the bloodstream (Hanahan& Weinberg., 2011). Metalloproteinases (MMPs) play a critical role in tumour migration, invasion and metastases via degradation of the extracellular matrix. Ecadherin is an important cell adhesion molecule. One study in human melanoma cells, showed that artemisinin was able to reduce MMP2 levels thereby blocking cell migration (Buommino *et al.*, 2009). In human pancreatic and ovarian cancer cells lines, DHA suppressed the levels of MMP2, inhibiting NF-κB and metastases (Wang et al., 2011; Wu et al., 2012). Similarly, artesunate was shown to abrogate MMPs and NF-κB activity, thereby blocking metastases in non-small cell lung cancer lines. Artemisinins downregulated the levels of MMP2 and TIMP-2 whilst up-regulating E-cadherin in hepatocarcinoma cells lines (Weifeng et al., 2011). Artesunate has been shown to upregulate the expression of adhesion molecules integrin β1 and neural cell adhesion molecule (NCAM) in embryonal rhabdomyosarcoma cells, thereby reducing migration and invasion (Beccafico *et al.*, 2015).

The Wnt/beta-catenin cell signalling pathway has been identified as a critical pathway in colorectal carcinogenesis (MacDonald *et al.*, 2009; Clevers *et al.*, 2006). Artesunate has been shown to inhibit the hyperactive Wnt/beta-catenin pathway in colorectal cancer cell lines, thereby attenuating cancer cell growth (Li *et al.*, 2008). The anticancer effects of artesunate on three colorectal cancer cell lines were compared and the relationship between drug sensitivity and malignant tumour phenotype analysed. In poorly-differentiated colorectal cancer cell line – CLY, beta-catenin accumulation and loss of E-cadherin was seen in the nucleus; in moderately-differentiated Lovo cells these two proteins accumulated in the cytoplasm; and in well-differentiated HT-29 cells beta-catenin and E-cadherin localized to the cell membrane. In vitro and in vivo, poorly- or moderately-differentiated CLY and Lovo cells were more susceptible to artesunate treatment than well-differentiated HT-29. The response of CLY and Lovo to artesunate were associated with membranous translocation of beta-catenin and increased expression of E-cadherin, which indicated the inhibition of the hyperactive Wnt/ $\beta$ -catenin signaling pathway and the reversion of the epithelial to mesenchymal transition, respectively. Artesunate has also been shown to induce apoptosis via inhibition of the Wnt/ $\beta$ -catenin pathway in myelodysplastic syndrome (MDS) cells (Xu *et al.*, 2015).

#### 6.8 Clinical evidence of anti-tumour effects of artesunate

A number of case reports have reported antitumour effects of artesunate in small groups of patients. One case study in a patient with laryngeal squamous cell carcinoma described a 70% reduction in tumor size after two months of artesunate treatment (Singh & Verma., 2002). Another case study reported a slowing of disease progression in a pituitary macroadenoma patient treated with artemether for 12 months (Singh & Panwar., 2006). Artesunate was also found to control tumor growth and improve survival in metastatic uveal melanoma (Berger et al., 2005). One patient with stage IV uveal melanoma experienced objective regression of splenic and lung metastases following the addition of artesunate to dacarbazine and remained alive 47 months after first diagnosis. An open label pilot study of dihydroartemisinin in 10 patients with advanced cervical cancer reported that treatment was well tolerated and improved patient symptoms (Jansen et al., 2011). A randomized controlled trial of artesunate in metastatic non small cell lung cancer randomised 60 patients to a control arm treated with doublet chemotherapy [intravenous vinorelbine (25mg/m²) on Day 1 and Day 8 and intravenous cisplatin (25mg/m^2) from Day 2-Day 4] and 60 patients treated with the same chemotherapy regime in addition to artesunate 120mg IV once daily from Day 1-Day 8 (Zhang et al., 2008). No statistically significant differences were seen in terms of the 1-year survival rate between the two treatment arms, although the disease control rate of the artesunate intervention group (88.2%) was significantly higher than that of the control group (72.7%) (P<0.05), and the artesunate arm's median time to progression (TTP) was significantly longer than that of the control arm (24 weeks vs 20 weeks) (P<0.05). No significant difference was found in toxicity between the two groups, including that of myelosuppression and gastrointestinal symptoms (P>0.05). A pharmaokinetic study of oral artesunate in 23 patients with metastatic breast cancer was also recently published (Ericcson et al., 2014). Survival data were not reported.

The first randomized placebo controlled double blind pilot study of artesunate in colorectal cancer randomized 23 patients with resectable colorectal cancer to receive either 14 daily doses of artesunate or placebo (Krishna et al., 2015). During a median follow up time of 42 months, 1 patient in the artesunate group developed recurrent colorectal cancer compared to 6 patients in the placebo group. Six patients receiving artesunate and 4 patients receiving placebo had measurable Carcinoma Embryonic Antigen (CEA) levels. Three patients in the placebo group had a rise in their CEA on rechecking their levels after the trial intervention whereas no patients in the artesunate group experienced a rise in their CEA levels (p=0.03). In one patient receiving artesunate there was a 75 % reduction in circulating CEA level after 2 weeks of artesunate treatment alone. Patients in the artesunate arm showed a high probability of a reduction in the ki67 proliferation index marker on tumour immunohistochemical analysis compared to those in the placebo arm. Artesunate was generally well tolerated apart from 2 cases of Grade 3 neutropenia and anaemia with one of the cases undergoing a spontaneous recovery of neutrophils and the other requiring granulocyte colony stimulating factor (GCSF). Both patients received a blood transfusion and went on to have surgery with no further complications.

#### 6.9 Summary

Artesunate is a safe and effective antimalarial with evidence of anticancer properties across a range of cancer cell lines. Results from our pilot feasibility study in colorectal cancer patients showed that artesunate was safe and well tolerated (Krishna *et al.*, 2015). These findings provided the basis for a Phase II clinical trial investigating the effects of neoadjuvant artesunate on progression free survival and overall survival (NeoART).

#### **6.10 Other treatments**

No other agents or treatments will be used in this study.

#### 6.11 Study Rationale and risk/benefit analysis

Neoadjuvant pre-operative chemotherapy is effective in a number of other cancer types supporting the theory that optimal neoadjuvant systemic therapy at the earliest opportunity may be more effective at eradicating distant metastases compared to adjuvant therapy delivered following the delay and immunological stress of surgery. Colorectal cancer metastases have a short doubling time (Tanaka *et al.*, 2004; Finlay *et al.*, 1988) and it has been postulated that micrometastatic tumour growth may be further accelerated in the early post operative period by enhanced growth factor activity (Zeamari *et al.*, 2004; Fahmy *et al.*, 2003; Schelfhout *et al.*, 2002). Neoadjuvant therapy also confers the potential advantage of primary tumour shrinkage, thereby reducing the risk of incomplete surgical excision and tumour shedding contaminating the surgical field during surgery (Nelson *et al.*, 2001). This may have particular relevance for transcoeliac spread with peritoneal metastases found in up to 50% of patients with locoregional relapse (Assersohn *et al.*, 1999). Neoadjuvant preoperative therapy in colorectal cancer started within days of diagnostic and staging investigations provides an unique treatment paradigm that could potentially eradicate micrometastases not managed with current standard treatment regimes.

Indeed, neoadjuvant combination chemotherapy with or wothout targeted anti- EGFR monoclonal antibody therapy with panitumumab forms the basis of the current FOxTROT trial (FOxTROT Collaborative Group., 2012). As previously mentioned however these regimens are associated with significant toxicities and surgery is often delayed whilst patients recover from these effects. These treatments are also expensive and remain economically out of reach for the majority of patients in developing countries.

There remains an urgent need to improve survival outcomes in patients with colorectal cancer globally using affordable interventions where possible. Artesunate has a good safety and tolerability profile, having been used to treat tens of millions of malaria patients globally. It is also relatively affordable at around £0.70 per daily dose. If neoadjuvant treatment with artesunate is found to reduce the risk of cancer recurrence and improve survival in operable colorectal cancer, this would be a practice- changing observation and would significantly improve care for millions of colorectal cancer patients worldwide.

#### 6.12 Assessment & management of potential risk

Participants who develop CTCAE v5.0, Grade 3 or 4 serious adverse effects related to artesunate (or placebo) will be withdrawn from the study treatment but will continue in the study to enable an intention to treat analysis. The main possible risks associated with artesunate in this phase II trial are neutropenia and haemolytic anaemia. Patients should be monitored closely for these potential side effects and sites should take appropriate clinical action if such adverse events occur.

Defination of aanemie is a disorder characterized by a reduction in the amount of haemoglobin in 100 ml of blood. Signs and symptoms of anaemia may include pallor of the skin and mucous membranes, shortness of

breath, palpitations of the heart, soft systolic murmurs, lethargy, and fatigability. Patients developing anaemia as defines by CTCAE 5.0

- Grade 3 anaemia: Hgb <8.0 g/dL; <4.9 mmol/L; <80 g/L; transfusion indicated

- Grade 4 anaemia: Life-threatening consequences; urgent intervention indicated

The treatment for anaemia is blood transfusion.

Definition of neutropenia: A disorder characterized by an ANC <1000/mm3 and a single temperature of >38.3 degrees C (101 degrees F) or a sustained temperature of >=38 degrees C (100.4 degrees F) for more than one hour. Patients developing neutropenia as defines by CTCAE 5.0

- Grade 3 neutropenia: ANC <1000/mm3 with a single temperature of >38.3 degree C (101 degrees F) or a sustained temperature of >=38 degrees C (100.4. degrees F) for more than one hour
- Grade 4 neutropenia: Life-threatening consequences; urgent intervention indicated

Treatment for neutropenia is GCSF.

There will be a 24 hour emergency card provided to each participant when they receive their IMP dispensed from pharmacy. The 24 hour emergency card will contain the contact details of the local PI and site team in addition to a NeoART-M 24 hour emergency telephone number.

The IMP will be supplied double-blinded and IMP allocation will be performed by each site pharmacy or clinical resarch centre in accordance with the randomisation list provided by the sponsor's representative at the start of the study. In the case of a medical emergency each Pharmacy or CRC will have the ability to unblind treatment.

The participating sites all have appropriate experience and knowledge of the target patient population. All team members will have demonstrated experience in clinical research and Good Clinical Practice (GCP).

The study is categorised 'Somewhat higher than the risk of standard medical care'. This would therefore require that IMP storage and accountability. The CI and the CI delegate will construct a Trial Master File and ensure that all essential trial documents are stored safely and securely. The trial will be subject to monitoring in accordance with the Sponsor risk-based monitoring plan. The purpose of the monitoring is to ensure the safety, rights and well being of the trial participants are upheld and that any risk to the trial data is minimised.

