#### 9.1 Inclusion criteria

- 1. Aged 18 or over
- 2. Histologically proven single primary site colorectal adenocarcinoma or high grade dysplasia plus unequivocal radiological evidence of invasive cancer
- 3. Stage II/III colorectal cancer planned for surgical resection and no clinical indication for neoadjuvant preoperative chemotherapy/chemoradiation therapy
- 4. WHO performance status 0,1 or 2
- 5. Adequate full blood count: White Cell Count (WCC)  $>3.0 \times 10^9$  /l; Platelets  $>100 \times 10^9$ /l; Haemoglobin (Hb) >80g/L
- 6. Adequate renal function: Glomerular Filtration Rate >30ml/min by Cockcroft-Gault formula.
- 7. Adequate hepatobiliary function: Total bilirubin < 3 x Upper limit norm
- 8. Female participants of child bearing potential must have a negative pregnancy test <72 hours prior to initiating study intervention and agree to avoid pregnancy using adequate, medically approved contraceptive precautions for up to 6 weeks after the last dose of study treatment interventions.
- 9. Male participants with a partner of childbearing potential must agree to use adequate, medically approved contraceptive precautions during and for up to 6 weeks after the last dose of the study treatment intervention.
- 10. Patient able and willing to provide writen, informed consent for the study.

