# 14. Pharmacovigilance

#### 14.1 Definitions

**Adverse Event (AE)** — Any untoward medical occurrence in a patient or clinical investigation subject administered a pharmaceutical product and which does not necessarily have to have a causal relationship with this treatment.

An adverse event (AE) can therefore be any unfavourable and unintended sign (e.g. an abnormal laboratory finding), symptom or disease temporally associated with the use of a medicinal product, whether or not considered related to the medicinal product. Pre-existing conditions should only be reported as an adverse event if the condition worsens by at least 1 CTCAE grade. As the IMP has a short half-life, we would expect drug clearance within 24 hours of stopping the IMP.

As part of pharmacovigilance, adverse event data will be collected from the day 1 of IMP dose until 4 weeks following the end of the IMP 14 day treatment schedule. This coincides with the D42 post surgical review.

**Adverse Reaction (AR)** — All noxious and unintended responses to a medicinal product related to any dose should be considered adverse drug reactions.

**Serious Adverse Event (SAE)** or Serious Adverse Reaction (SAR) — any untoward medical occurrence that at any dose:

- Results in death,
- Is life-threatening,
- Requires inpatient hospitalisation or prolongation of existing hospitalisation,
- Results in persistent or significant disability/incapacity or
- Is a congenital anomaly/birth defect.

Medical and scientific judgement should be exercised in deciding whether expedited reporting is appropriate in other situations, such as important medical events that may not be immediately lifethreatening or result in death or hospitalisation but may jeopardise the patient or may require intervention to prevent one of the other outcomes listed in the definition above. These should also usually be considered "serious".

Suspected Unexpected Serious Adverse Reaction (SUSAR) — an Adverse Reaction which is classed in nature as both serious and unexpected

An 'Unexpected Adverse Reaction' is when both the nature and severity of the event is not consistent with the reference safety information available for the IMP in question.

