#### 15.2 Data collection tool

Case Report Forms will be designed by the CI and the CI delegate and the final version will be approved by the Sponsor.

It is the Investigator's responsibility to ensure the accuracy of all data entered and recorded in the CRFs. The Staff Delegation of Responsibilities Log will identify all trial personnel responsible for data collection, entry, handling and managing the database. Basic demographic and clinical information will be gathered at the time of the initial interview and by review of the medical notes if needed. The following information will be recorded for all subjects in the CRF:

- Demographic details: Date of enrolment, age, gender, ethnicity
- Clinical data: symptomatology, risk factors for development of CRC, weight, height, vital signs
- Findings at endoscopy
- Imaging: findings of ultrasound, CT and/or MRI (performed as clinically indicated)
- Disease staging: TNM staging prior to surgery and definitive histological staging (TNM, Duke's stage)
- Histology: routine histological grading, apoptosis count and specialist assays (see below)
- Concomitant medication: a full record of all non-study drugs taken will be kept
- Study-drug treatment: compliance with study medication, all adverse events, serious or otherwise
- Validated Quality of Life Tool (EORTC QLQ C-30, EuroQol EQ-5D, QLQ-CR29)

The following blood sample analysis will be performed:

- Baseline FBC, urea and electrolytes, LFTs, CEA, pre-treatment serum sample for study molecular analyses
- Day 14/15 of treatment FBC, urea and electrolytes, LFTs, CEA, post-treatment serum sample for study molecular analyses
- Day 28 FBC
- Day 42 (4 weeks post-surgery) FBC, urea and electrolytes, LFT, CEA
- 6 monthly visits for 5 years following surgery CEA
- Serum plasma samples will be taken at baseline (Day 1) and end of treatment (Day 14), processed and stored at -80°C (+/- 10°C) for future analyses
- Any other blood or clinical sample at any time if deemed necessary by the investigators in case of a suspected adverse event

All laboratory analysis should be reviewed by the PI and where results reported are not within the normal range the PI must clearly annotate 'Not clinically Significant' or 'Clinically Significant' and sign and date the results. The relevant results should be carefully transcribed to the Case Report Forms.

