#### Toxicity assessments

The proportion of patients experiencing grade 3 or 4 toxicity will be compared between the two treatment arms using the chi-squared test. When cell frequencies are less than 5, Fisher's exact test will be used. The chi-squared test for trend will also be used to compare all toxicity scores.

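### The planned toxicity tests use CTCAE grades alone, over a window that spans surgery, and are insensitive to a modest haemoglobin fall

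*Protocol*

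**What the plan says.** Protocol section 6.12 states: "The main possible risks associated with artesunate in this phase II trial are neutropenia and haemolytic anaemia". It then gives the grade limits, among them "Grade 3 anaemia: Hgb <8.0 g/dL; <4.9 mmol/L; <80 g/L; transfusion indicated".

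Section 17.3.3.3, under Toxicity assessments, fixes two comparisons. The first is "The proportion of patients experiencing grade 3 or 4 toxicity will be compared between the two treatment arms using the chi-squared test", with Fisher's exact test for small cells. The second is "The chi-squared test for trend will also be used to compare all toxicity scores". No comparison of haemoglobin as a measured value is described, and no time window is set for the toxicity grades.

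Three other places bear on what those tests will see:

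- Section 14.1 collects adverse events from the first dose until four weeks after the 14-day course, which it equates with the Day 42 review. Surgery is on Day 15. The section also says: "Pre-existing conditions should only be reported as an adverse event if the condition worsens by at least 1 CTCAE grade".
- Section 14.2 lets a mildly deranged blood test of no clinical significance go without an adverse-event form or log entry.
- Section 15.2 lists "Baseline FBC, urea and electrolytes, LFTs, CEA, pre-treatment serum sample for study molecular analyses" and "Day 14/15 of treatment FBC, urea and electrolytes, LFTs, CEA, post-treatment serum sample for study molecular analyses", then further full blood counts at Day 28 and Day 42. Section 12.3 requires the safety bloods to be available before surgery.

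Eligibility (section 9.1) requires "Haemoglobin (Hb) >80g/L".

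**The concern.** Haemolytic anaemia is one of two risks that the protocol singles out, and section 6.8 reports two Grade 3 neutropenia and anaemia cases in the pilot, both transfused. The quantity at risk is continuous and is measured in every patient just before and just after treatment. The planned tests reduce it to a grade, which discards every fall that stays within a grade.

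The adverse-event window adds noise. Grades that arise after Day 15 can reflect operative blood loss in either arm, and this dilutes a difference that arose during the 14 treatment days. The trend test also depends on lower grades being recorded, which section 14.2 does not guarantee for mild laboratory changes if the toxicity scores come from adverse-event data.

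At stake is how a null result is read. A non-significant toxicity table could be taken as reassurance on haemoglobin when the tests had little chance of showing a modest fall.

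**Working it through.** **Inputs from the protocol.** 200 patients (section 7.1), 1:1 (section 11.2), so 100 per arm; 5% level (section 17.2.1), taken as two-sided; Grade 3 anaemia below 80 g/L (section 6.12); eligibility above 80 g/L (section 9.1).

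**The plan's own figure.** The protocol states no power for toxicity or haemoglobin. Its only sample size is for recurrence, and it reproduces: D = (1.28 + 0.842)² / (0.25 × (ln 0.56)²) = 4.503 / 0.0840 = 53.6, so 54 events; N = 53.6 × 100/32, which rounds up to 168. The 100 per arm therefore comes from the primary endpoint.

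**Assumed inputs.** The documents give no haemoglobin distribution. Assumed: baseline SD 18 g/L truncated at 80, mean 105–125; within-patient SD of change 8–12; true drug effect −5 or −10 g/L; lower grade cut-points 125 and 100 g/L, because the CTCAE table is not reproduced.

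**Step 1. Grade 3/4 proportion alone.** Power = Φ{[|p1 − p0| − 1.96√(2p̄(1 − p̄)/n)] / √[p0(1 − p0)/n + p1(1 − p1)/n]}, n = 100. For 2% v 5%: [0.03 − 1.96 × 0.0260] / 0.0259 = −0.81, power 21%. Likewise 5% v 10% gives 27%, 10% v 20% gives 51%, and 2% v 10% gives 67%. For 80% power the artesunate rate must reach about 12.5% (placebo 2%), 17.5% (placebo 5%) or 25% (placebo 10%).

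**Step 2. Baseline-adjusted haemoglobin.** SE = SD × √(2/100). With SD 8: 1.13, and Φ(5/1.13 − 1.96) = 0.99. With SD 12: 1.70, and Φ(5/1.70 − 1.96) = 0.84.

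**Step 3. All methods by simulation.** 1,500 runs per setting; Fisher for small cells; trend as a Cochran–Armitage test on grades 0–3. The worsened column scores a grade only if it exceeds the baseline grade, as in section 14.1.

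| Fall (g/L) | Baseline mean | Within-patient SD | Grade 3/4 | Trend | Trend, worsened | ANCOVA |
|---|---|---|---|---|---|---|
| 5 | 110 | 8 | 11% | 43% | 63% | 99% |
| 5 | 110 | 12 | 15% | 39% | 48% | 84% |
| 5 | 120 | 8 | 2% | 40% | 57% | 99% |
| 5 | 120 | 12 | 5% | 34% | 41% | 82% |
| 5 | 125 | 8 | 0% | 38% | 52% | 100% |
| 5 | 125 | 12 | 2% | 32% | 40% | 82% |
| 10 | 110 | 8 | 62% | 95% | 100% | 100% |
| 10 | 110 | 12 | 56% | 90% | 96% | 100% |
| 10 | 120 | 8 | 20% | 93% | 99% | 100% |
| 10 | 120 | 12 | 23% | 87% | 94% | 100% |
| 10 | 125 | 8 | 5% | 91% | 99% | 100% |
| 10 | 125 | 12 | 12% | 86% | 93% | 100% |

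Repeated with baseline means of 105–115, a 5 g/L fall gives about 6–20%, 36–49%, 44–65% and 85–99%. ANCOVA agrees with step 2 within simulation error.

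**Step 4. Incomplete recording.** Take mean 115, within-patient SD 8 and a 5 g/L fall. If half of Grade 2 and a tenth of Grade 1 worsenings were logged (an assumption), power of the trend test on worsened grades drops from 59% to 32%.

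**Step 5. Does the shared 80 g/L limit cause this?** With an 8 g/L fall, mean 115 and within-patient SD 8, Grade 3/4 power is about 20–22% with the eligibility floor at 80, about 22% at 70, and about 4% at 90. Separating the limits upwards makes the test weaker. The cause is rare events and coarse grades.

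**The case against.** The plan does not rest on Grade 3/4 alone. The trend test uses every grade, so a fall from 130 to 85 g/L is visible to it, and for a 10 g/L fall it has about 86–95% power. Section 14.1 brings baseline in by requiring a one-grade worsening. All of this stands. A reader might infer that the trial cannot see a haemoglobin effect at all; the documents do not support that.

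A reader might also infer that the result is driven by who was anaemic at entry, because eligibility ends where Grade 3 begins and a fall from 81 to 79 g/L counts. Nobody may enter at or below 80 g/L, so any Grade 3 value is a fall from the qualifying value. Randomisation against placebo balances baseline haemoglobin in expectation, so leaving it out costs precision and does not bias the comparison. With a baseline mean of 115 and SD 18, about 0.8% of patients would enter at 80–82 g/L (200 × 0.008 = 1.6 patients), and step 5 shows that the shared limit is not the cause. The two limits are not an inconsistency.

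The last objection is that laboratory models and shift tables are usual SAP content, and that safety interim analyses and DMC review are planned. This limits the point but does not remove it. The protocol itself fixes the toxicity tests under its heading Statistical analysis plan, and what it fixes is grade-only. If a separate SAP already adds a haemoglobin comparison, only a cross-reference is missing.

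**Conclusion.** The point holds as a minor one about precision. For a modest fall of about 5 g/L, both planned tests and the worsened-grade variant are well short of a baseline-adjusted comparison: 0–20%, 32–49% and 40–65% against 82–100% across all settings run. For a fall of about 10 g/L the planned trend test is adequate if grades are fully recorded, and the gain is small.

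The haemoglobin distribution, within-patient SD, effect sizes, lower cut-points and recording rates are all assumptions; the documents give none of them, and state no fall that would matter clinically. The ordering of the methods for a 5 g/L fall was the same in every setting. The simulation does not model operative blood loss, so the effect of the window to Day 42 is argued from the schedule and not quantified.

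**What to change.** In section 17.3.3.3, keep the Grade 3/4 comparison and the trend test, and add:

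- an ANCOVA of pre-operative Day 14/15 haemoglobin on treatment arm with baseline haemoglobin as covariate, reporting the adjusted mean difference with its 95% confidence interval;
- a table by arm of grade shifts from baseline to Day 14/15, graded from the laboratory values so that it does not depend on adverse-event logging.

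The Day 14/15 sample covers the treatment period before operative blood loss. The cost is a few lines of analysis text: no new samples or visits, and no change to eligibility or patient care. If a separate SAP already contains this analysis, a cross-reference from 17.3.3.3 is enough.

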#### 8.6 Concomitant treatment

There are no reports of negative drug interactions with artesunate to date. Concomitant medication details will be collected at baseline and any changes recorded at subsequent study visits.

We will document adjuvant treatment following surgery such as chemotherapy and aspirin therapy. We will include this in our final data analysis in order to account for any confounding results that could arise as a result of adjuvant therapy. If patients develop Grade 3 neutropenia or more (according to the Common Terminology Criteria for Adverse Events (CTCAE) Version 5.0) Definition of neutropenia: A disorder characterized by an ANC <1000/mm3 and a single temperature of >38.3 degrees C (101 degrees F) or a sustained temperature of >=38 degrees C (100.4 degrees F) for more than one hour. Grade 3 neutropenia: ANC <1000/mm3 with a single temperature of >38.3 degree C (101 degrees F) or a sustained temperature of >=38 degrees C (100.4. degrees F) for more than one hour. They should be managed with granulocyte colony stimulating factor (GCSF) supplied via routine hospital pharmacy in accordance with local policy and prescribing practice.

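### Sections 6.12 and 8.6 make fever part of neutropenia and its Grade 3, and nothing says whether this text or the appended CTCAE v5.0 governs, so afebrile low counts may be graded inconsistently

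*Protocol*

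**What the plan says.** Section 6.12 names neutropenia and haemolytic anaemia as the main possible risks of artesunate. It then gives this definition: "Definition of neutropenia: A disorder characterized by an ANC <1000/mm3 and a single temperature of >38.3 degrees C", with a sustained temperature of at least 38 degrees C for more than one hour as the alternative to the single reading. Grade 3 carries the same count and the same fever condition. The only other printed grade is "Grade 4 neutropenia: Life-threatening consequences; urgent intervention indicated". The section introduces these grades as those of CTCAE 5.0 and adds "Treatment for neutropenia is GCSF".

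Section 8.6 repeats the definition and the Grade 3 line directly after its own citation of the standard: "If patients develop Grade 3 neutropenia or more (according to the Common Terminology Criteria for Adverse Events (CTCAE) Version 5.0". Of such patients it says "They should be managed with granulocyte colony stimulating factor (GCSF) supplied via routine hospital pharmacy".

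The anaemia entry in Section 6.12 is built differently at Grade 3: "Grade 3 anaemia: Hgb <8.0 g/dL; <4.9 mmol/L; <80 g/L; transfusion indicated". It sets a haemoglobin threshold and requires no accompanying sign.

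The grade is used in three places:
- Section 17.3.3.3 (Toxicity assessments) compares the proportion with Grade 3 or 4 toxicity between arms and applies a chi-squared trend test to all toxicity scores.
- Section 8 (Dosage modifications) stops trial treatment for a related Grade 3/4 reaction by CTCAE v5.0.
- Section 8.6 triggers GCSF.

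CTCAE v5.0 is listed as Appendix 4, but only its title is in the text at hand.

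**The concern.** By the words of Sections 6.12 and 8.6, a patient with a very low neutrophil count and a normal temperature has neither neutropenia nor a Grade 3 event. The protocol watches for this toxicity mainly by blood count, so afebrile low counts are what its scheduled tests would find. If some sites grade from the body text and others from the appended criteria, the same laboratory result receives different scores in a comparison that pools three countries. Where the body text is followed, afebrile cases score as no neutropenia in both toxicity tests. Any loss would fall more heavily on the arm with more low counts. Neutropenia matters here: it is a named main risk, and Section 8 calls it dose-limiting at 6 mg/kg daily, although the trial's own dose is stated as 2 to 4 mg/kg.

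**Working it through.** The protocol gives no expected neutropenia rate and no power for toxicity, so there is no figure to reproduce. The check compares the text in several places, followed by simple arithmetic.

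**1. What the body text can grade**
- Printed neutropenia grades: 2 (Grade 3 in Sections 6.12 and 8.6, Grade 4 in Section 6.12 only).
- Grades resting on the count alone: 0 of 2. Grade 3 needs fever; Grade 4 needs life-threatening consequences.
- The missing count at Grade 4 and the absence of lower grades are not peculiar to neutropenia, because the anaemia list has the same form. The contrast that counts is at Grade 3, where anaemia is graded by the laboratory value and neutropenia is not.

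**2. What the schedule measures** (Sections 12.2, 12.3 and 15.2, Appendix 2)
- Scheduled full blood counts after baseline: 3 (Day 14/15, Day 28, Day 42).
- Of these, with a scheduled temperature: 0 of 3. Vital signs appear at screening (Appendix 2) and baseline (Section 12.2) only.
- A low count on any of these three tests therefore cannot be graded under the printed definition without a temperature that is not scheduled.

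**3. How the protocol treats neutropenia elsewhere**
- Section 6.8 reports from the pilot "2 cases of Grade 3 neutropenia and anaemia with one of the cases undergoing a spontaneous recovery of neutrophils". It describes the course by neutrophils and GCSF and does not mention fever. This is silence, not proof that the patients were afebrile.
- Section 11.4 lists neutropenic sepsis as an emergency in its own right, so the complicated form already has a separate name.

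**4. Effect on discontinuation**
- Scheduled post-baseline counts before Day 14: 0. Last dose: Day 14 (Section 12.3). The scheduled tests come too late to stop much treatment, whichever definition is used. An unscheduled test for a suspected adverse event (Section 15.2) could matter in single patients.

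**5. Size per case**
- 200 randomised 1:1 gives 200/2 = 100 per arm. One ungraded afebrile case with no other Grade 3/4 event lowers that arm's proportion by 1/100 = 1 percentage point.
- Pilot: 2 cases among 23 randomised, 2/23 = 8.7%; arm sizes and temperatures are not given. Both also had anaemia, and "Both patients received a blood transfusion and went on to have surgery with no further complications". They might have counted as Grade 3 through anaemia. In such patients the any-Grade-3/4 proportion is unchanged and only neutropenia itself is missed.

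**6. Direction, under assumed rates**

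The rates and febrile shares below are assumptions, not in the protocol. The table treats neutropenia alone, with 100 per arm, the same febrile share in both arms and a two-sided Fisher test at 0.05. The counted rate is the true rate times the febrile share.

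| True rates of ANC <1000/mm3 | All cases count | 50% febrile | 25% febrile | 10% febrile |
|---|---|---|---|---|
| 10% vs 1%: counted per 100 | 10 vs 1 | 5 vs 0.5 | 2.5 vs 0.25 | 1 vs 0.1 |
| power | 0.77 | 0.27 | 0.03 | about 0 |
| 15% vs 3%: counted per 100 | 15 vs 3 | 7.5 vs 1.5 | 3.75 vs 0.75 | 1.5 vs 0.3 |
| power | 0.82 | 0.40 | 0.10 | <0.01 |

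This shows only that counting febrile cases alone reduces both the count and the power. It does not estimate the loss in this trial.

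**The case against.** The strongest reply is that the protocol names a grading standard. Sections 6.12, 8 and 8.6 cite CTCAE v5.0, Section 14.1 uses its grades for worsening of pre-existing conditions, and the criteria are appended. A trained site may simply grade from Appendix 4. Section 17.3.3.3 does not refer to Section 6.12 or 8.6, which deal with risk management and GCSF. Out-of-range results are annotated by the site's principal investigator and relevant ones go to the CRF (Section 15.2). An abnormal laboratory finding can be an adverse event (Section 14.1). Counts could therefore be re-graded at analysis.

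Much of this stands, and it rules out several stronger readings:
- *An afebrile low count has no grade anywhere in the protocol.* Not established: the grade may be in Appendix 4, which cannot be seen.
- *The printed definition departs from CTCAE v5.0.* Not shown by these documents, for the same reason.
- *Section 12.3 contradicts the definition by using a blood count to exclude neutropenia.* It does not: a normal count excludes a condition that requires a low one.
- *UK and Vietnamese patients were graded by another rule, because the amendment log dates the definitions to July 2024.* Section 17.3.2 calls the three studies mirror studies, and the other two protocols are not shown.
- *The toxicity result will be biased.* That depends on sites following the body text.

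What does not stand is that Appendix 4 settles the matter. Sections 6.12 and 8.6 present the fever-based wording as the CTCAE definition, so a site has no reason to look further, and no rule says which text prevails.

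**Conclusion.** The point holds as a body-text definition that requires fever and may compete with the appended standard, with no rule on which governs. Inconsistent grading and some understatement of neutropenia in the Grade 3/4 comparison and the trend test are risks, not certainties. They rest on the assumption that at least some sites grade by Sections 6.12 and 8.6.

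The size cannot be estimated, because the protocol gives neither a neutropenia rate for this trial nor a febrile share. The arithmetic bound is 1 percentage point per affected patient with no other Grade 3/4 event. Discontinuation is little affected, the counts are recoverable, and the primary analysis is untouched. Severity is minor to should-fix: the harm is limited, but the rule misgrades a named main risk if followed as written.

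**What to change.** - In Sections 6.12 and 8.6, grade neutropenia by neutrophil count with no fever condition, and take the thresholds for each grade from Appendix 4 after checking the text against it.
- List febrile neutropenia as a separate term.
- State that the count-based grade governs adverse event grading and the toxicity analysis.
- Set the GCSF trigger as a separate clinical decision, for example febrile neutropenia only or local policy. Reword "Treatment for neutropenia is GCSF" in Section 6.12 and the matching instruction in Section 8.6 to agree with it. Otherwise the new definition would extend GCSF to every afebrile count in the Grade 3 range.

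The cost is wording in two sections. No new tests are needed, because the blood counts at Day 14/15, 28 and 42 are already scheduled. Reported toxicity may look slightly less favourable, and the clinical team must commit to a GCSF trigger.
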